5.1 Minimized risks to participants

45 CFR 46.111 (a) 1 and 21 CFR 56.111 (a) 1: Risks to subjects are minimized.

This protocol minimizes risks to participants by (a) correctly and promptly informing participants about risks so that they can join in partnership with the researcher in recognizing and reporting harms; (b) respecting local/national blood draw limits; (c) performing direct observation of participants postvaccination and reporting information regarding side effects to the FDA/CDC Vaccine Adverse Event Reporting System (VAERS) per EUA guidance; (d) having staff properly trained in administering study procedures that may cause physical harm or psychological distress, such as blood draws, vaccinations, COVID-19 testing and counseling; and (e) providing safety monitoring.

5.2 Reasonable risk/benefit balance

45 CFR 46.111(a) 2 and 21 CFR 56.111(a) 2: Risks to subjects are reasonable in relation to anticipated benefits, if any, to subjects, and the importance of the knowledge that may reasonably be expected to result.

In all public health research, the risk-benefit ratio may be difficult to assess because the benefits to participants in prevention protocols are not as apparent as they would be in treatment protocols, where a study participant may be ill and may have exhausted all conventional treatment options. However, this protocol is designed to minimize the risks to participants while maximizing the potential value of the knowledge it is designed to generate.

5.3 Equitable participant selection

45 CFR 46.111 (a) 3 and 21 CFR 56.111 (a) 3: Subject selection is equitable

This protocol has specific inclusion and exclusion criteria for investigators to follow in admitting participants into the protocol. Participants are selected because of these criteria and not because of positions of vulnerability or privilege. Investigators are required to maintain screening and enrollment logs to document volunteers who screened into and out of the protocol and for what reasons.

5.4 Appropriate informed consent

45 CFR 46.111 (a) 4 and 5 and 21 CFR 56.111 (a) 4 and 5: Informed consent is sought from each prospective subject or the subject's legally authorized representative as required by 45 CFR 46.116 and 21 CFR Part 50; informed consent is appropriately documented as required by 45 CFR 46.117 and 21 CFR 50.27

The protocol specifies that informed consent must be obtained before any study procedures are initiated and assessed throughout the trial (see Section 9.1). Each site is provided training in informed consent by the CoVPN and is required to have a Standard Operating Procedure (SOP) on the informed consent process. The CoVPN requires a signed consent document for documentation, in addition to chart notes or a consent checklist.

5.5 Adequate safety monitoring

45 CFR 46.111 (a) 6 and 21 CFR 56.111 (a) 6: There is adequate provision for monitoring the data collected to ensure the safety of subjects.

Vaccination providers are required to report to VAERS the certain adverse events after COVID-19 vaccination, under Emergency Use Authorization (EUA) and encouraged to report adverse events to ModernaTX (<https://www.cdc.gov/vaccines/covid-19/vaccination-provider-support.html>, see Section 11). Additionally, the use of v-safe will be recommended to vaccine recipients (<https://www.cdc.gov/coronavirus/2019-ncov/vaccines/safety/vsafe.html>, see Section 11), and an Independent Data Monitoring Committee (IDMC) will periodically review study data.

5.6 Protect privacy/confidentiality

45 CFR 46.111 (a) 7 and 21 CFR 56.111 (a) 7: There are adequate provisions to protect the privacy of subjects and maintain the confidentiality of data.

Privacy refers to an individual's right to be free from unauthorized or unreasonable intrusion into his/her private life and the right to control access to individually identifiable information about him/her. The term "privacy" concerns research participants or potential research participants as individuals whereas the term "confidentiality" is used to refer to the treatment of information about those individuals. This protocol respects the privacy of participants by informing them about who will have access to their personal information and study data (see [Appendix A](#), [Appendix B](#), [Appendix C](#) and [Appendix D](#)). The privacy of participants is protected by assigning unique identifiers in place of the participant's name on study data and specimens. In the United States, research participants in CoVPN protocols are protected by a Certificate of Confidentiality from the US NIH, which can prevent disclosure of study participation even when that information is requested by subpoena. Participants are told of the use and limits of the certificate in the study consent form. In addition, each staff member at each study site in this protocol signs an Agreement on Confidentiality and Use of Data and Specimens with the CoVPN. In some cases, a comparable confidentiality agreement process may be acceptable. Each study site participating in the protocol is required to have a standard operating procedure on how the staff members will protect the confidentiality of study participants.

6 Statistical considerations

With an overall goal of accruing 48,000 person-months divided evenly between vaccinated and unvaccinated follow-up time, we anticipate enrolling up to 18,000 participants. Up to 12,000 participants will be randomized 1:1 to Immediate Vaccination Group (at Months 0 and 1) or Standard of Care Group, with vaccination given at Months 4 and 5 if not received off-study previously. Up to an additional 6,000 participants will be enrolled into the Vaccine Declined Group and will also be offered vaccine at Months 4 and 5. Operational monitoring of SARS-CoV-2 incidence, retention, outside COVID-19 vaccination, adherence to study procedures, and enrollment and testing of contacts in the PCC and CACC – *pooled over main study participant groups* – will guide the choice of total number randomized and total number in the Vaccine Declined Group. Guidelines will be specified in the study SAP.

Primary analyses of vaccine efficacy against infection (VE_S) and of the vaccine effect on viral load (Δ VL) will be conducted among all main study participants SARS-CoV-2 seronegative at enrollment. These analyses will be supported by analyses in the “Day 29 Negative Set”—the set of participants without PCR-confirmed infection on or prior to Day 29—that only count SARS-CoV-2 infection events diagnosed post-Day 29; see [Table 6-1](#) for a full definition of the various analysis sets for the study. Secondary analyses will be conducted among all participants who receive both immunizations, ie, the Per-Protocol Set. Immunogenicity assessment will be done in the Case-Cohort Immunogenicity Set—a subsample of the participants randomized to immediate vaccination and sampled on the basis of SARS-CoV-2 infection status and baseline characteristics that will be fully described in the study SAP.

The FAS differs from a full Intention-to-Treat set by excluding randomized volunteers who do not enroll. The exclusion of these individuals is justified because the effects of the vaccine are unlikely to influence such exclusion. Because of the brief length of time between randomization and enrollment (ideally these will be on the same day), we expect almost all randomized volunteers to be in the FAS.

All primary and secondary analyses will be done according to enrollment group, ie, Immediate Vaccination Group, Standard of Care Group, or Vaccine Declined Group.

Main study participants will be tested using real-time PCR testing of swabs, and these data will be used to identify SARS-CoV-2 infection events for primary analysis. Some main study participants may also receive SARS-CoV-2 testing through university testing systems, or through outside providers, and will be asked to report any positive test results to the study team. Any positive SARS-CoV-2 test results for main study participants – based on PCR testing of study swabs or based on other testing systems indicative of acute infection – will trigger

swabbing of contacts in the PCC and enrollment and swabbing of contacts in the CACC. Secondary analyses of vaccine efficacy will include SARS-CoV-2 infection events diagnosed through any testing system – either by PCR testing of study swabs or through outside testing.

The two contact cohorts – the PCC and the CACC – will both be used for analyses of the vaccine effect on secondary transmission, as described below.

The study is “time-driven”, ie, the primary analysis will occur when all participants have completed the 4 months follow-up. The number of primary endpoint infection events that accrue in the study is random and will depend on the level of SARS-CoV-2 incidence in each arm.

Table 6-1 Study Analysis Sets and Definitions

Analysis Set	Definition	Analyses
Full Analysis Set (FAS)	Main Study participants who enroll in the study	Primary efficacy analyses*
Day 29 Negative (D29-) Set	Participants in the FAS without PCR-confirmed infection on or before Day 29 ⁹	Primary efficacy analyses*
Per-Protocol (PP) Set	Participants in the D29- set who received all planned immunizations at the designated immunization visits within specific visit windows	Secondary efficacy analyses*
Day 29 Negative Transmission Set (D29-TS)	Participants in the D29- set and their contacts in the Prospective and Case Ascertained Contact Cohorts	Primary analyses of secondary transmission*
Case-Cohort Immunogenicity Set (ccIS)	Subset of the FAS that is randomly sampled for measurement of immunological markers and fully described in study SAP	Immunology marker analyses

*These analysis sets include participants without regard to baseline SARS-CoV-2 status. However, primary

efficacy analyses will condition on baseline SARS-CoV-2 seronegative status.

⁹Note that Day 29 is the second vaccination visit (visit 3) for participants on the Immediate Vaccination Group. The SAP will specify the definition of Day 29 for participants in the Standard of Care Group and in the Vaccine Declined Group.

Table 6-2 Assumptions underlying study power/sample size calculations, unless otherwise specified. Parameters and their assumed values pertain to participants in the main study cohort.

Parameter	Assumption
Enrollment	Uniform enrollment over 4 weeks
Baseline seroprevalence in main study and PCC and CACC	10% of enrolled participants are baseline SARS-CoV-2 seropositive. This parameter is monitored and controlled operationally (see Section 6.3)
Per-protocol rate	98% of enrolled participants are in the per-protocol set
Loss to follow-up rate in the main study, the PCC and the CACC	5% of participants are lost to follow-up over 16 weeks at a constant rate
SARS-CoV-2 incidence absent vaccination	Exponential (constant rate) over 16 weeks; primary assumption is 4% over 16 weeks

Secondary transmission rate among susceptible contacts absent vaccination	15% transmission rate based on (47-49)
Vaccine efficacy (VE) against SARS-CoV-2 infection and transmission	Constant after 14 days post-first vaccination (calculations do not depend on earlier VE); level is varied
Contact enrollment	For the PCC: 60% of main study participants enroll contact(s) and the average number of contacts enrolled is 2 For the CACC: 75% of main study participants enroll contact(s) and the average number of contacts enrolled is 3

6.1 Accrual and sample size calculations

Sample size calculations were performed assuming that 48,000 person-months of follow-up will accrue, evenly divided between vaccinated and unvaccinated follow-up time and subject to a small 5% loss-to-follow-up rate. This person-time may come entirely from 12,000 participants randomized to Immediate Vaccination Group versus Standard of Care Group and followed for 4 months (16 weeks), or, if there is insufficient unvaccinated follow-up among those randomized to Standard of Care, it will be supplemented with unvaccinated follow-up for participants in the Vaccine Declined Group. The power calculations apply, regardless of where the unvaccinated follow-up comes from. For this reason, we refer to the two groups being compared as “vaccinated” and “unvaccinated”, where the former group consists of participants randomized to immediate vaccination and the latter group may include both participants randomized to Standard of Care Group and participants enrolled in the Vaccine Declined Group (see [Figure 2-7](#)).

Power calculations also focused conservatively on numbers of infections that accrue post-Day 29, although as mentioned above, primary analyses will be conducted both in the FAS, counting all follow-up and infection events post-enrollment; and in the Day 29 negative set, counting only follow-up and infection events post-Day 29.

With 48,000 person-months of follow-up, evenly divided between vaccinated and unvaccinated follow-up, there is a high probability that a sufficient number of post-Day 29 infection events, ie, SARS-CoV-2 infections among baseline seronegative participants in the D29- set and diagnosed after Day 29, will accrue to adequately power analyses addressing both primary objectives as well as key secondary objectives. Specifically, with 24,000 person-months of vaccinated follow-up and 24,000 person-months of unvaccinated follow-up, under a 4% SARS-CoV-2 incidence absent vaccination over 16 weeks (a conservative assumption for US college campuses, see [Section 2.5](#), and supported by unpublished modeling within the CoVPN), assuming $VE_S = 50\%$ and other assumptions laid out in [Table 6-2](#), a total of 225 post-Day 29 infection events will occur across vaccinated and unvaccinated groups with probability 0.5 and 214 events will occur with probability 0.8.

Table 6-3 shows the expected number of post-Day 29 infection events in the main study cohort overall and in the vaccinated group, as the assumed incidence absent vaccination varies. As shown, the design ensures a sufficient number of post-Day 29 infection events to address a variety of objectives that condition on post-Day 29 infection. For example, with 4% SARS-CoV-2 incidence absent vaccination, 75 post-Day 29 infection events are expected in the vaccinated group for immune correlates analyses.

Table 6-3 Expected number of post-Day 29 infection events, available for secondary analyses that condition on event status. Calculations assume 24,000 person-months of vaccinated follow-up and 24,000 person-months of unvaccinated follow-up and other assumptions in Table 6-2, $VE_S = 50\%$, and varying 16-week incidence of SARS-CoV-2 infection absent vaccination.

16-Week SARS-CoV-2 Background (unvaccinated) Incidence	Post-Day 29 Infection Events	
	Vaccinated and Unvaccinated Groups Combined	Vaccinated Group
1.5%	86	28
2%	143	47
3%	170	56
3.5%	198	66
4%	225	75

The study provides high power to evaluate the vaccine effect on acquisition (VE_S). Figure 6-1 shows the power of the study to detect a given level of VE_S , rejecting $H_0: VE_S \leq 30\%$, based on a 1-sided 0.025-level log-rank test and as a function of the SARS-CoV-2 incidence absent vaccination. With 4% 16-week incidence, the study has 90% power to detect any $VE_S > 57\%$; with 3% incidence, $VE_S > 60\%$ can be detected with 90% power.

The proposed study also provides adequate precision with which to estimate VE_S . Table 6-4 shows that, with 225 post-Day 29 infection events, the approximate 95% confidence interval (CI) about an estimated 50% VE_S is (36.9%, 60.4%). More precise inference is obtained under higher VE_S and higher post-Day 29 infection totals.

[figure not shown]

Figure 6-1 Power to detect varying vaccine efficacy (VE) against SARS-CoV-2 infection as a function of incidence absent vaccination over 16 weeks. Simulation-based power calculations assume 24,000 person-months of vaccinated and 24,000 person-months of unvaccinated follow-up and other assumptions listed in [Table 6-2](#). Power based on 1-sided 0.025-level log-rank test and 1,000 simulations.

Table 6-4 Approximate 95% confidence interval around a given estimated VEs against SARS-CoV-2 infection, comparing vaccinated and unvaccinated groups as a function of the number of post-Day 29 infection events in the vaccinated and unvaccinated groups. Calculations assume 24,000 person-months of follow-up in each group and other assumptions in [Table 6-2](#).

Number of post-Day 29 infection events	Approximate 95% CI for estimated VE = 50%	Approximate 95% CI for estimated VE = 70%
200	(36.0%, 60.9%)	(60.7%, 77.2%)
225	(36.9%, 60.4%)	(61.1%, 76.9%)
250	(37.7%, 59.9%)	(61.6%, 76.6%)

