
7. To evaluate immune responses 1 month post-second vaccination as correlates of risk of SARS-CoV-2 acquisition, viral load, secondary infection, and COVID-19 disease among vaccine recipients in the Immediate Vaccination Group
	
Magnitude and response rate of immune responses to vaccination in the Immediate Vaccination Group and measured at Months 0 and 2, stratified by baseline SARS-CoV-2 serostatus, as measured by binding antibody and neutralization assays in the case-cohort immunogenicity set

8. To evaluate vaccine efficacy against asymptomatic SARS-CoV-2 infection
	
SARS-CoV-2 infection by PCR or periodic serology among participants seronegative for SARS-CoV-2 at baseline and without any prior reporting of symptoms that led to confirmation of a COVID-19 disease endpoint

9. To evaluate vaccine efficacy against SARS-CoV-2 infection and COVID-19 disease and the vaccine effect on viral load and secondary transmission among participants who received all planned immunizations at the designated immunization visits within specific visit windows
	
Endpoints evaluated among participants who were SARS-CoV-2 seronegative at enrollment
 
 • SARS-CoV-2 infection diagnosed by PCR [Primary endpoint 1] • Peak log10 viral load in nasal samples from participants who are diagnosed with SARS-CoV-2 infection [Primary endpoint 2] • Number of secondary transmission events in the PCC and CACC [Secondary endpoint 1] • SARS-CoV-2 infection coincident with signs and symptoms of COVID-19 listed under Secondary endpoint 3

10. To evaluate the association between measures of the magnitude of viral load over time and secondary transmission of SARS-CoV-2 infection, among individuals with incident SARS-CoV-2 infection in each treatment group, i.e. to conduct analyses aimed at evaluating viral load measures as surrogates of secondary transmission
	
 • Peak log10 viral load [Primary endpoint 2] and other viral load summaries [Secondary endpoints 4] • Number of secondary transmission events in the PCC cohort and CACC cohort [Secondary endpoint 1]

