6.4.6 Immunogenicity analyses

6.4.6.1 Vaccine immunogenicity

Immunogenicity will be characterized for the immediate vaccination group only, using data from the Case-Cohort Immunogenicity Set (ccIS). Data from quantitative immunogenicity assays will be summarized using positive response rates and geometric means with 95% CIs, for each timepoint for which an assessment is performed. Data from qualitative (ie, yielding a positive or negative result) assays will be summarized by tabulating the frequency of positive responses for each assay at each timepoint that an assessment is performed. Analyses focus on the Month 2 time point, the Day 1 time point, and the change in marker response between the two time points. The analyses will evaluate immunogenicity in all immediate vaccination arm participants and separately in subgroups defined by baseline SARS-CoV-2 serostatus. The SAP will describe the complete set of immunogenicity analyses.

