Appendix E Procedures for Main Cohort, Immediate Vaccination Group

Visit:	01 ¹	02 ²	03	04	05	06
Day:		D1	D29	D57	D113	D141
Week:		W0	W4	W8	W16	W20
Month:		M0	M1	M2	M4	M5
Procedure	Scr.	VAC1	VAC2			
Study procedures						
Screening consent (if used)	✓	—	—	—	—	—
Assessment of understanding	✓	—	—	—	—	—
Protocol consent (eConsent)	✓	—	—	—	—	—
Medical history questionnaire ³	✓	✓	—	—	—	—
SARS-CoV-2 infection risk assessment ³	✓		Weekly			
COVID-19 symptom surveillance ³	—		Weekly starts at week 2, not during week 5			
Confirm eligibility	✓	—	—	—	—	—
Obtain demographics ³	✓	—	—	—	—	—
Randomize	—	✓	—	—	—	—
SARS-CoV-2 testing questionnaire ³	—		approximately 2x per week			
End of study questionnaire ³	—	—	—	—	✓	—
Research Samples⁴						
Serum for Immunogenicity Assays and Storage	—	✓	—	✓	—	—
Serum for SARS-CoV-2 clinical serology ⁵	—	✓ ⁶	—	✓ ⁶	✓	—
Nasal swab	—		Daily ⁷			
Vaccination procedures						
COVID-19 symptom check ⁸	—	✓	✓	—	—	—
Vaccination	—	✓	✓	—	—	—

Greyed out visit column does not apply to this group.

1 Screening may occur over the course of several contacts/visits up to and including day 1, prior to vaccination.

2 Blood draws required at vaccination visits must be performed prior to vaccination.

3 Results from screening at school, if applicable, or at other locations will be captured via eDiary, please see Section 9.16.

4 From screening to the final study visit, the total blood volume to be collected from each participant will be approximately 40 mL (maximum) with a maximum of approximately 17 mL collected in a single visit.

5 For blood self-collected by a participant the maximum volume will be less than 1 mL in a single collection.

6 SARS-CoV-2 clinical serology testing may be performed on leftover blood from samples collected for immunogenicity assays. No separate blood sample is needed. If a Main cohort participant is also in the Prospective Close Contact (PCC) cohort related to

an index case or in the Case-ascertained Close Contact (CACC) cohort, one additional blood collection (self-collection) will be performed (see table below).

7 Daily swabs will be collected from vaccination through D113. Swabs will be returned via drop-off location(s) specified by the clinic or through the mail.

8 COVID-19 Symptom Check to be performed within 24 hours prior to vaccination.

The following **additional** procedures will occur for Main cohort, immediate vaccination participants, who fall under any of the following categories:

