2.5 Sample Size and Power

At the design stage, sample size calculations assumed 48,000 person-months of follow-up (even between vaccinated and unvaccinated, with the latter potentially including the Vaccine Declined group), 5% loss-to-follow-up rate, 10% baseline sero-positivity, 98% per-protocol rate, SARS-CoV-2 infection endpoint post Day 29 among baseline seronegative participants in the D29- set with 4% event incidence over 16 weeks (constant over time) among unvaccinated. Under these assumptions, the study had 90% power to detect $VE > 57\%$ using one-sided 0.025-level log-rank test. Additionally, assuming 50% VE we expected (50% probability) at least 225 post-Day 29 events to be available to estimate the vaccine effect on mean peak log10 viral load. The assumed 225 events, SD in peak log10 viral load = 1.8 (equal in both arms), 1-sided 0.025-level two-sample t-test yielded 96.9% power.

Due to early termination of the trial, the study is underpowered to address primary study objectives.

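### Of the 75 vaccinated-group infections the protocol expects for immune correlates, only about 50 fall after the Month 2 marker is drawn

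*Protocol*

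**What the plan says.** Protocol section 6.1 presents Table 6-3 as showing that enough post-Day 29 infections will accrue for objectives that condition on infection. Its worked example is the correlates analysis: at 4% incidence, "75 post-Day 29 infection events are expected in the vaccinated group for immune correlates analyses".

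The objective served is secondary objective 7 (Protocol section 3): "To evaluate immune responses 1 month post-second vaccination as correlates of risk of SARS-CoV-2 acquisition, viral load, secondary infection, and COVID-19 disease". It is confined to the arm vaccinated at enrollment. Dose 2 is scheduled on D29, so one month later is Month 2, D57.

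The sampling schedule agrees. In Appendix E the row "Serum for Immunogenicity Assays and Storage" is ticked at D1 and D57 only. Section 9.3 takes specimens at the first vaccination visit but not the second, and the version history records that the Month 1 blood collection was removed for this group. Section 6.4.6.1 states: "Analyses focus on the Month 2 time point, the Day 1 time point, and the change in marker response between the two time points". Daily swabs, which define the PCR endpoint, stop at D113 (Appendix E, footnote 7).

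Correlates methods are left to a separate document, called the Trial Marker SAP in Protocol section 6.4.6.2 and the Immune Correlates SAP in SAP section 8.

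**The concern.** A correlate of risk relates a marker measured in an uninfected participant to infection afterwards. The 75 starts counting at D29, four weeks before the marker exists. For someone infected between D29 and D57, the Month 2 sample is taken after infection and may reflect the infection as well as the vaccine. The Day 1 sample cannot stand in for it, because it precedes vaccination. The extra serum after a positive test cannot either: it is for clinical serology and is also drawn after infection.

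At stake is the only event count that section 6.1 offers for objective 7. A reader judging whether the design can support that objective would start from a number that includes infections the marker cannot predict.

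**Working it through.** **Inputs.**
- Table 6-2, incidence without vaccination: "Exponential (constant rate) over 16 weeks; primary assumption is 4% over 16 weeks". Vaccine efficacy is constant from 14 days after dose 1, so the vaccinated hazard is flat from D29 on.
- Table 6-2 also gives 10% baseline seropositive, a 98% per-protocol rate and 5% loss over 16 weeks.
- Table 6-3: "Calculations assume 24,000 person-months of vaccinated follow-up and 24,000 person-months of unvaccinated follow-up". Over 4 months that is 24,000/4 = 6,000 participants per group. Efficacy is 50%.
- Days since enrollment (D1 is t = 0): D29 is t = 28, D57 is t = 56, D113 is t = 112.

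**Reproducing the stated figure.**
- Hazard without vaccine: λ = −ln(0.96)/112 = 0.000364 per day. Vaccinated: λ₁ = λ/2 = 0.000182 per day.
- With the 5% loss removed at the start: n = 6,000 × 0.90 × 0.98 × 0.95 = 5,027.
- Taking no efficacy in the first 14 days (the choice hardly matters here), the fraction of the vaccinated group uninfected at t = 28 is exp(−14λ − 14λ₁) = 0.9924.
- Vaccinated infections after D29: 5,027 × 0.9924 × [1 − exp(−84λ₁)] = 75.8.
- Unvaccinated infections after D29: 5,027 × [exp(−28λ) − exp(−112λ)] = 150.0.
- Total: 225.8.

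This matches 75 and 225 in Table 6-3 and the 225 in SAP section 2.5 ("assuming 50% VE we expected (50% probability) at least 225 post-Day 29 events"). Table 6-7 gives medians of 75 to 76 vaccinated and 150 unvaccinated at this efficacy. Spreading the loss evenly over time gives 77.3 vaccinated counting from t = 28, or 76.3 from t = 29. The 75 is sound as a post-Day 29 count.

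**Counting from the marker.**
- By proportion: D29 to D113 is 84 days and D57 to D113 is 56 days, so 75 × 56/84 = 50. The other 75 × 28/84 = 25 precede the draw.
- By the exponential model, loss removed at the start: uninfected at t = 56 is exp(−14λ − 42λ₁) = 0.9873, and 5,027 × 0.9873 × [1 − exp(−56λ₁)] = 50.4.
- With loss spread over time: 51.1.

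All three give about 50, two thirds of the stated count. The same proportion applies to the other incidence rows; at 3%, for example, 56 × 56/84 = 37.

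**The case against.** The sentence labels its count as post-Day 29, and that count is right, so there is no arithmetic error. It is also an illustration, and section 6.1 gives no power, precision target or minimum number of events for correlates. The vaccinated-group column of Table 6-3 runs from 28 to 75 and the whole table is offered as showing enough events; 50 lies within it. No stated power or precision result uses the Month 2 marker, so none changes. The counting rule may already stand in the correlates SAP, which is not among the documents. And SAP sections 2.4 and 2.5 say that the randomized part stopped early for operational futility and that the study is underpowered for its primary objectives, so the design figure no longer drives a decision.

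Most of this stands, and it limits the point to a figure attached to the wrong use. It does not remove it. The sentence ties the 75 to immune correlates by name, and a separate SAP can set a counting rule but cannot supply a post-vaccination immunogenicity sample before D57. The SAP's remarks on early stopping do not correct the number.

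**Conclusion.** The figure 75 is correct for infections after Day 29 and too high for the use stated. About 50 vaccinated-group infections follow the Month 2 draw at 4% incidence and 50% efficacy. This rests on the constant hazard of Table 6-2, draws on the target day, and no minimum gap between draw and infection. Late draws or a required gap would lower it. A late Month 4 visit would not raise it, because swabbing stops at D113.

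A reader might infer more than the documents support:
- **That the design fails objective 7.** No sufficiency threshold for correlates is stated, so failure cannot be shown.
- **That standard errors rise by √(75/50) = 1.22, or 22%.** Markers are measured in a case-cohort sample whose control numbers section 6 leaves to the SAP. With, say, 150 controls held fixed (an assumption), the factor is √[(1/50 + 1/150)/(1/75 + 1/150)] = 1.15.
- **That the expected count ranges from about 38 to 56.** Those totals (75 × 42/84 and 75 × 63/84) need every participant drawn on D71 or every participant on D50. Appendix I sets limits for individual visits, not for the expected total.
- **That the 15 vaccinated-group transmissions in Table 6-7 shrink to 10.** The protocol offers those 15 for efficacy against transmission between groups, not for correlates.

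**What to change.** In Protocol section 6.1, say that about 50 infections after the Month 2 draw are expected in the vaccinated group for immune correlates, at 4% incidence and 50% efficacy, with draws on the target day, and that late draws or a minimum gap would reduce this. Keep 75 for analyses that count from Day 29.

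Confirm that the separate correlates SAP counts only infections diagnosed after the participant's actual Month 2 sample; if it does not, add that rule there.

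The cost is wording only. Sample size, visits and data collection do not change. The stated figure becomes less favourable. Since the trial has stopped, the practical use is that any report on correlates should quote the design expectation that matches its marker.
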